## 6.6 Estatistical analysis

Data on demographic, socioeconomic, medical and criminal history, as well as on pre, intra and post-intervention laboratory tests will be stored online at REDCap, available at <<http://www.matogrossodosul.fiocruz.br/redcap/>>, where each researcher is identified by single user and password, guaranteeing restricted and confidential access. Statistical analysis will be done with IBM® SPSS Statistics software.

The incidence will be calculated on the basis of the new cases detected during the follow-up period, per 100 person-years. It will be considered a new case of TB individuals, regardless of the group, who present bacilloscopy or positive culture. For latent TB, a seroconversion will be considered for individuals who exhibit interferon gamma levels above the upper limit considered by the manufacturer of the QuantiFERON® TB Gold Plus commercial test in the 12th or 24th month.

The effect of the intervention will be calculated through Relative Risk (RR), considering a Confidence Interval of 95% (95% CI). To determine the effectiveness of the intervention will be used Relative Risk Reduction (RRR) and Absolute Risk Reduction (RAR). In addition, to measure the impact of the intervention, the Number Needed to Treat (NNT) will be calculated.

Two protocols will be performed for statistical analysis: 1) intention-to-treat analysis and 2) per protocol. The sample calculation for the primary outcomes is based on intention-to-treat analysis.

The intent-to-treat analysis will be performed for all subjects who complete at least 6 months of treatment. The participant may decide to withdraw the consent in whole or in part. In the case of withdrawal of partial consent IGRA will be withdrawn at the 12th or 24th month and the participant will remain in the study according to the initial randomization.

Analysis by protocol will be performed only using the group of individuals who completed at least 80% of the predicted doses of the study.

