#### 6.1.1 Sample and population of the study

This research will be carried out at one prison unit, located in the city of Dourados, in the state of Mato Grosso do Sul. Currently, this prison unit has approximately 2,300 inmates, with a mean age of  $31.5 \pm 9.4$  years; an average of  $9.7 (\pm 4.2)$  individuals per cell, who remain in a closed regimen, about  $20.8 (\pm 24.1)$  months. The TB indicators show a tuberculin test seroconversion rate of 26% (23-26) and incidence, 2.45 / 100,000(28).

The sample was calculated for a significance level of 5%, detection power of 90%, considering a percentage of occurrence of latent TB of 20% in the control group after one year of follow-up and 10% in the experimental group. For these parameters, 560 individuals will be needed for the study, however, 30% will be added for possible losses, ending the sample in 728 participants. Memory calculation available at <https://www.sealedenvelope.com/power/binary-superiority/>.

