## 6.4 Indications for premature exclusion

The participant may be withdrawn from the clinical trial at any time for the reasons listed below:

- at the request of the participant (withdrawal or withdrawal of consent);
- non-compliance with the protocol;
- interruption of treatment or sum of temporary interruptions of intervention  $\geq 90$  days, either by decision of the participant or at medical discretion;
- transfer to another prison unit or early release;
- Clinical or laboratory AE requiring permanent discontinuation of medication (according to study-specific SOP);
- any exclusion criterion according to item 5.3 that, incidentally, arises during the follow-up (both recently diagnosed and not previously recognized);
- use of acetaminophen, valproic acid, carbamazepine, cycloserine, ethionamide, corticosteroids, diazepam, triazolam, disulfiram, phenytoin, aluminum hydroxide and rifampicin which, at the discretion of the investigator, are used in a dose that may interfere with the efficacy of INH as medication;
- another reason, at the discretion of the principal investigator or study coordinator.

At the time of the participant's withdrawal, a premature exclusion visit with clinical evaluation, evaluation of AE and blood and / or sputum collection should be performed according to the clinical judgment, according to the study schedule (figure 1).

In addition, for cases in which treatment has been interrupted by decision of the participant or at medical discretion, as of 6 months from the start of the DOT, the participant will have two options: to remain in the study without the intervention (DOT), but with the accomplishment of all the visits anticipated in the protocol or to leave completely of the study without the realization of

additional collections and other accompaniments. For the latter case, follow-ups will be carried out only if the participant presents some AE at the time of their withdrawal.

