## 6.5 Conducting the study

Participants will be invited to participate in the clinical trial through the consent process and will agree to participate in the study by signing the ICF.

In the recruitment interval, prior to any intervention, participants will respond to the AUDIT questionnaire - which assesses various levels of alcohol use, from safe use to likely dependence - and eligibility criteria will be checked. In the recruitment interval, participants will have a 9mL sample of peripheral blood collected for testing of IGRA (QuantiFERON® TB GOLD PLUS kit - Qiagen, HIV, hepatitis B (HBsAg) and C (Anti-HCV) and serum levels of liver enzymes (AST and ALT).

After the results of these initial tests (HIV, hepatitis B and C, IGRA, AST and ALT), if eligible, the participant will answer questionnaires containing socioeconomic, medical and criminal history and have a sample of sputum collected for culture.

The participant will be included in the study without the result of the culture and, in case of a positive result for Mtb, the intervention will be suspended, the same will be excluded from the study and treated according to the MS protocol. If the sputum culture is contaminated, a new sample should be collected within 30 days after the result.

The recruitment interval will last 20 to 45 days.

On the day of initiation of DOT (D0), each participant will receive a supervised dose (three oral tablets) of INH (900mg) or placebo. The same will happen twice a week for 12 months. During the DOT the participant will be asked about AE.

Blood samples will be collected every three months after D0 to measure hepatic enzyme levels (AST and ALT), as well as clinical evaluation and verification of AE, as shown in figure 1.

At six months and at the end of the intervention (12th month), all participants will have a sample of sputum collected for culture and a blood sample for detection / quantification of interferon gamma. The same evaluation will be repeated in the 24th month counted from D0, that is, one year after the end of the intervention.

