At follow-up visits of 6, 12 and 24 months, if the interferon gamma result is indeterminate, the participant remains in the clinical trial and a new sample is collected within 30 days. If the IGRA result is positive (result standardized according to the package insert of the Qiagen®), the participant will suspend the medication (in the case of the 6-month visit), will be excluded from the study and treatment for latent TB.

If the sputum culture is positive for Mtb, the participant will be excluded from the study and treatment for active TB according to MS will be offered. If the sputum culture is contaminated, a new sample should be collected within 30 days after the result.

In the occurrence of hepatotoxicity, diagnosed through hepatic enzyme levels (elevation greater than five times the upper limit of the test if the individual is asymptomatic) and / or clinical examination (presence of jaundice, right upper quadrant pain, dark urine, fever, asthenia, myalgia), the intervention will be interrupted and the participant will be led to clinical care by the project team, according to the project's SOP. In this study, the following values will be used as laboratory parameter: AST: 8-40 IU / mL and ALT: 5-30 IU / mL(54,55). Other laboratory tests may be

requested from the research participants, according to the clinical judgment of the physician responsible for the care of the AE and according to the specific SOP of the project.

IGRA, smear culture, and serology for HIV, hepatitis B and C are performed LPCS / UFGD. The AST/ALT exams and other laboratory tests, when necessary, are performed in an external laboratory.

During the course of the study, the Notification of Injury Information System will be used to identify the occurrence of active TB cases in both groups.

The box below summarizes the activities to be developed at each stage of the protocol.

	Enrollment	DOT start (D0)	1 st visit (3 mo± 15 d)	2 nd visit (6 mo± 15 d)	3 rd visit (9 mo± 15 d)	4 th visit (12 mo± 30 d)	5 th visit (24 mo± 30 d)	Early exclusion visit
Consent process	X							
Verification of inclusion and exclusion criteria	X							
AUDIT	X							
Medical history	X							
Criminal history	X							
Randomization		X						
DOT star		X						
DOT end						X		
IGRA	X			X		X	X	(X)
ALT, AST	X		X	X	X	X		(X)
Another laboratory exams	(X)		(X)	(X)	(X)	(X)		(X)
Anti-HIV, HBsAg e Anti-HCV	X							(X)
Sputum coleccion	X			X		X	X	(X)

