## 6.7 Interim analysis

After a 6-month visit of at least 100 participants, in addition to the follow-up clinic-laboratorial evaluation (which includes blood collection for hepatic enzyme dosage and directed clinical examination), an evaluation of the effectiveness of the intervention will be carried out, through sputum culture and interferon-gamma dosing / quantification. It is estimated that there is a linear relationship between follow-up time and the risk of acquisition of latent TB.

This evaluation intends to verify the feasibility of continuity of the study and adequacy of the sample calculation. The study will be discontinued if the primary endpoint is less than 2.5% as compared to the control group, or if the difference between the intervention group and the control group is greater than 12.5% according to the box below:

	Intervention (isoniazid) (N=162)	Control (placebo) (N=162)	Finale total number (N final+30%)
Reference	5.0%	10%	726
Insufficient sample	7.5%	10%	3357
Insufficient sample	10.0%	12.5%	3910
Insufficient sample	12.5%	15.0%	4555
Insufficient sample	15.0%	17.5%	5114
Insufficient sample	17.5%	20.0%	5361
Sufficient sample	5.0%	17.5%	172
Sufficient sample	7.5%	20.0%	187
Sufficient sample	10.0%	22.5%	213
Sufficient sample	12.5%	25.0%	218
Sufficient sample	15.0%	27.5%	229

Figura 2 - Sample table of the sample values in both groups (intervention and control), based on the primary outcome.

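### The seroconversion definition in section 6.6 leaves out the scheduled month-6 IGRA, against the interim analysis and the basis of the sample size

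*Combined protocol and SAP*

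**What the plan says.** Section 6.6 is the only place that defines a latent-TB event for analysis. It names readings above the manufacturer's limit on the QuantiFERON "TB Gold Plus commercial test in the 12th or 24th month". Month 6 is not named.

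Section 6.5 schedules the test earlier as well: "At six months and at the end of the intervention" all participants give blood for interferon gamma, and again at month 24. On a positive result, section 6.5 says "the participant will suspend the medication (in the case of the 6-month visit), will be excluded from the study and treatment for latent TB".

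The sample size in section 6.1.1 rests on "latent TB of 20% in the control group after one year of follow-up and 10% in the experimental group". Section 5.1 states the primary outcome as a halving of latent TB after 12 months.

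Section 6.7 says that, once at least 100 participants have had the 6-month visit, "an evaluation of the effectiveness of the intervention will be carried out, through sputum culture and interferon-gamma dosing / quantification". Figure 2 is captioned as giving "sample values in both groups (intervention and control), based on the primary outcome", and the section assumes that "there is a linear relationship between follow-up time and the risk of acquisition of latent TB".

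Section 6.6 also restricts the intention-to-treat set to participants with at least 6 months of treatment, and the per-protocol set to those with at least 80% of planned doses.

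**The concern.** A participant who converts by month 6 is found by a planned study test, is then excluded under section 6.5, and does not meet the event definition in section 6.6. On the plan's linear-risk assumption this applies to half of all first-year conversions. The interim analysis treats the same conversions as primary-outcome data. Two analysts could therefore work from the same protocol and report different event counts, absolute effects and p-values for the primary outcome. The two analysis sets add to the doubt, because neither definition says where a participant stopped for a positive month-6 IGRA belongs.

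**Working it through.** **Inputs.** 20% vs 10% at one year, 5% significance, 90% power, 560 before losses and 728 after (6.1.1); 364 per arm (6.1.2); linear risk and the Figure 2 rates (6.7). The documents do not state sidedness; two-sided is assumed.

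**1. The plan's own sample size.** With p̄ = 0.15 and d = 0.10:

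n = [1.960·√(2·0.15·0.85) + 1.282·√(0.20·0.80 + 0.10·0.90)]² / 0.10² = 265.9 per arm.

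With continuity correction, n' = (n/4)·[1 + √(1 + 4/(n·d))]² = 285.5, rounded up to 286 per arm, or 572 in total. That is within about 2% of 560, and 560 × 1.3 = 728. The stated figures stand for 20% vs 10%.

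**2. What Figure 2 implies.** The same formula, total × 1.3, was applied to the rates as printed and to the rates doubled from 6 to 12 months.

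| INH vs placebo, as printed | Stated | Doubled | Not doubled |
|---|---|---|---|
| 5% vs 10% | 726 | 744 | 1615 |
| 7.5% vs 10% | 3357 | 3255 | 7181 |
| 10% vs 12.5% | 3910 | 3910 | 8931 |
| 15% vs 17.5% | 5114 | 4893 | 12100 |
| 15% vs 27.5% | 229 | 229 | 621 |

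Over all 11 rows, doubling gives totals within -4.3% to +2.4% of those stated. Without doubling they are 114% to 171% too high. The table therefore takes month-6 conversions as half of a cumulative 12-month risk.

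**3. Events under the literal definition.** Linear risk puts 10% vs 5% at month 6. At 280 per arm, first-year conversions are 56 + 28 = 84, of which 28 + 14 = 42 occur by month 6 and are not counted.

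**4. Power.** Power = Φ[(d - 1.960·s₀)/s₁], with s₀ the pooled (null) and s₁ the unpooled standard error of the difference.

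- *Month 6 counts:* 20% vs 10%. At 280 per arm, s₀ = 0.03018 and s₁ = 0.02988, so Φ(1.367) = 91%. At 364 per arm, 97%.
- *Month-6 positives leave the analysis:* 0.10/0.90 = 11.1% vs 0.05/0.95 = 5.26%, with arms of 0.90n and 0.95n (252 and 266). d = 0.0585, s₀ = 0.02400, s₁ = 0.02407, so Φ(0.476) = 68%. At 364 per arm, 79%.
- *Month-6 positives kept as non-events:* 10% vs 5%. d = 0.05, s₀ = 0.02226, s₁ = 0.02216, so Φ(0.287) = 61%. At 364 per arm, 73%.

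**5. Effect measures named in 6.6.**

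| | Month 6 counts | Positives leave | Kept as non-events |
|---|---|---|---|
| RR | 0.50 | 5.26/11.1 = 0.47 | 0.50 |
| Absolute risk reduction, points | 10 | 5.8 | 5.0 |
| NNT | 10 | 17 | 20 |

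**6. Analysis sets.** A participant stopped at month 6 of a 12-month course has had about half the planned doses, so the 80% rule removes every such converter from the per-protocol set. The month-6 visit has a window of ±15 days, so one stopped slightly early could also miss the 6-month condition for intention-to-treat.

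**The case against.** The best defence is that section 6.6 is incomplete rather than contradictory. It does not say that a month-6 positive is a non-event, and the intended reading can probably be recovered from section 6.7. Much of this stands. Figure 2 does point to a cumulative 12-month endpoint that includes month 6. But doubling an interim rate is an extrapolation and not a counting rule, and the one sentence that defines the event leaves month 6 out. The primary definition should not have to be inferred from an interim table.

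Four stronger readings are tempting, and the documents do not support them.

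- *That several sections expressly count month-6 conversions.* Only section 6.7 does so directly. Section 6.1.1 never mentions month 6; it conflicts only because section 6.5 takes these participants out. The incidence sentence in 6.6, based on new cases during follow-up, points the same way but is general, and can be read as governed by the definitions that follow it.
- *That the estimated relative effect would be seriously wrong.* The RR stays at 0.47 to 0.50.
- *That the trial will have 61% power.* That needs known converters to be kept as non-events, which no text instructs. Removal, at 68%, follows more naturally from section 6.5.
- *That section 6.4 rescues the month-6 positives*, because some participants whose treatment is interrupted may choose "to remain in the study without the intervention (DOT), but with the accomplishment of all the visits anticipated in the protocol". That option covers interruption by the participant's decision or at medical discretion. Section 6.5 is specific to a positive IGRA and says exclusion. The documents give no basis for assuming that any share stays and is retested.

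**Conclusion.** The point holds as a defect in the primary event definition that must be corrected. Section 6.6 conflicts directly with section 6.7 and, through the exclusion in 6.5, with the one-year risks behind the sample size. The harm falls on the event count, power, absolute risk reduction and NNT; the relative risk is nearly unaffected.

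The power loss, from 91% to between 61% and 68% at 280 per arm and from 97% to between 73% and 79% at 364, is conditional. It assumes that 6.6 is followed literally, that month-6 positives leave under 6.5, that risk is linear as the plan states, that 20% vs 10% is true, and that the test is two-sided at 5%. Other losses are ignored. If month 6 is counted, the stated sample size needs no change on this account.

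**What to change.** In section 6.6:

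- Define the 12-month primary event as the first positive IGRA at month 6 or month 12, counted in the randomised arm.
- Report conversions between months 12 and 24 separately, as the outcome for the residual-effect aim in section 4.2.
- State that the 6-month treatment condition for intention-to-treat does not remove a participant whose treatment stopped because of a positive month-6 IGRA.
- State the same for the 80%-of-doses condition for per-protocol, with doses judged up to the stop.

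Then reconcile sections 5.1, 6.5, 6.6 and 6.7 with this definition. No change to the clinical handling of positives is proposed.

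The cost is a protocol amendment rewording 6.6, since the trial is registered and ethics-approved (6.9). The month-6 IGRA is already collected, so no data, visits or participants are added.

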## 6.3 Exclusion criteria

- Be indigenous;
- Active TB or previous use of INH;
- Sscore AUDIT  $\geq 15$ .
- Reactive serology for HIV, hepatitis B and C;
- Reactive result for IGRA, considering as positive the result of TB1 Tube and / or TB2 Tube above 0.2 IU/mL(53);
- Liver enzymes (AST and ALT) three times the upper limit;
- History or treatment for epilepsy;

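### Section 6.6 names no baseline covariates for the primary relative risk; the unadjusted estimate is valid, but pre-specified adjustment would add a little precision and protect against chance imbalance at almost no cost

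*Combined protocol and SAP*

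**What the plan says.** On the primary effect, section 6.6 says "The effect of the intervention will be calculated through Relative Risk (RR), considering a Confidence Interval of 95% (95% CI"). It adds relative and absolute risk reduction (ARR) and the number needed to treat (NNT). It names no regression model, test or covariate, and no adjusted analysis appears elsewhere. That the RR is unadjusted is inferred from this silence; the text does not use the word.

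Section 6.1.2 describes simple randomisation of 364 participants to each arm, with no stratification factor.

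Three kinds of baseline information exist before the first dose:

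- **Interferon-gamma.** Section 6.3 excludes people on the baseline IGRA, "considering as positive the result of TB1 Tube and / or TB2 Tube above 0.2 IU/mL". Applying that rule needs a numeric reading for each tube, and everyone enrolled is at or below 0.2 IU/mL in both.
- **Age.** Section 6.2 restricts entry to ages above 18 and under 45.
- **Criminal history.** Section 6.5 says that, once eligible, "the participant will answer questionnaires containing socioeconomic, medical and criminal history". The individual items are not listed.

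Section 6.6 places demographic data, criminal history and pre-intervention laboratory results in the study database.

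**The concern.** A baseline measurement on the same assay as the endpoint is a natural covariate, and incarceration history is a plausible marker of exposure. If such variables predict conversion, an RR that ignores them has a wider interval than it needs. It also carries any chance imbalance in them straight into the estimate.

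Simple randomisation keeps the arms comparable on average, but neither strata nor the analysis deals with the imbalance that happens to occur in this one trial. Because 6.6 is silent, any adjusted RR produced after the randomisation list is opened (6.1.3) would be a post hoc choice, and there could be a dispute over which RR counts.

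**Working it through.** **1. The plan's own figure.** Section 6.1.1 assumes "considering a percentage of occurrence of latent TB of 20% in the control group after one year of follow-up" and "10% in the experimental group", with 5% significance (two-sided assumed, since sidedness is not stated) and 90% power, and concludes that "560 individuals will be needed for the study".

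- Log-RR formula, per arm: (1.96 + 1.282)² × (0.9/0.1 + 0.8/0.2) / (ln 2)² = 10.51 × 13 / 0.480 = 285 after rounding up, or 570 in total.
- Two-proportion test: 532 without and 572 with continuity correction.
- The stated 560 is within 3% of 570 and 572. Power at 280 per arm is 91.4% (pooled test) or 89.6% (log-RR Wald).
- 560 × 1.3 = 728, as stated.

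**2. Precision without adjustment.** SE(log RR) = √(13/n). At 280 per arm this is 0.2155, so a true RR of 0.50 has an expected 95% CI of 0.328 to 0.763.

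**3. Gain from adjustment.** The documents give no predictive strength, so one standardised normal covariate is assumed, with OR per SD from 1.0 to 2.5. Let m1(x) and m0(x) be the logistic risks in the two arms, calibrated to average 0.10 and 0.20. For a standardised RR with 1:1 allocation, the large-sample fraction of variance removed is

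Var[m1(X)/0.10 + m0(X)/0.20] / [2(0.9/0.1) + 2(0.8/0.2)] = Var[...] / 26.

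For moderate ORs the numerator is close to (0.9 + 0.8)² × (ln OR)² = 2.89 (ln OR)², which gives a hand check. Power is Φ(ln 2 / SE − 1.96).

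| OR per SD | Var[...] | Variance removed | Power gain, 255 per arm (points) | Power gain, 280 per arm (points) |
|---|---|---|---|---|
| 1.0 | 0 | 0% | 0 | 0 |
| 1.25 | 0.14 | 0.5% | 0.2 | 0.2 |
| 1.5 | 0.47 | 1.8% | 0.6 | 0.5 |
| 1.8 | 0.99 | 3.8% | 1.2 | 1.1 |
| 2.5 | 2.29 | 8.8% | 2.9 | 2.5 |

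Simulation agrees within its error. With 2,500 trials per scenario at 280 per arm, the adjusted-to-unadjusted variance ratio was 0.994 at OR 1.25, 0.975 at 1.5 and 0.924 at 2.5. The simulated power of the usual tests rose by 0, 0.2 and 1.7 points, so the figures above are not understated. With a useless covariate the ratio was 1.001, which means no measurable loss.

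At OR 1.8 the SE becomes 0.2155 × √0.96 = 0.211 and the expected CI is 0.331 to 0.756, against 0.328 to 0.763 without adjustment.

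**4. Chance imbalance.** The SD of a standardised mean difference between arms is √(2/n): 0.085 at 280 per arm and 0.074 at 364. A two-SD imbalance at 280 per arm is about 0.17 SD. With OR 1.8 per SD, the slope on the log-risk scale is about ln 1.8 × 0.85 = 0.588 × 0.85 = 0.50. The log RR then shifts by about 0.17 × 0.50 = 0.085, and a true RR of 0.50 is estimated around 0.50 × e^0.085 = 0.54, or 0.46 in the other direction. Adjustment for that covariate removes the shift.

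**5. Can the data carry the model?** At 280 per arm the expected events are 56 + 28 = 84. Arm plus three covariates is four terms, or 21 events per term.

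**The case against.** The strongest reply is that nothing is wrong with the planned estimate. Under simple randomisation the unadjusted RR is unbiased on average, and its confidence interval already allows for chance imbalance, which is small at this size. That stands. A reader might infer from the missing covariates that the primary result would be biased or its error rate wrong; the documents do not support that.

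Second, the benefit may be close to nil. No document gives a predictive strength. Interferon-gamma is cut off at 0.2 IU/mL and age is confined to a band, so two of the three candidates have lost part of their range. Incarceration keeps more spread: section 6.1.1 gives 20.8 months with an SD of 24.1 in this prison. This stands too, and it is why the range must include ORs of 1.5 and below.

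Third, a reader might take 728 × 0.7 = 510 as the planned evaluable number, note that pooled-test power at 255 per arm is 88.8%, and present adjustment as the way to recover the stated 90%. The documents do not support that. Section 6.1.1 adds 30% to 560, so 168 of 728 (23%) can be lost with 560 remaining. Whether that allowance is adequate is a separate sample-size question, and covariate adjustment is not its remedy. The 255-per-arm column above serves only as a sensitivity case.

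Fourth, adjustment needs care. The logarithm of a zero interferon-gamma value is undefined, the content of the criminal-history questionnaire is not described, and missing covariates need a rule. These points shape the fix but do not remove the case for it.

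**Conclusion.** The point holds as an inexpensive improvement. The plan specifies no covariate adjustment, has no stratification, and collects suitable baseline data. Pre-specified adjustment would remove about 0-2% of the variance of log RR at OR 1.0-1.5 per SD, about 4% at 1.8 and about 7-9% at 2.5. In power this is about 0-0.5, 1-1.5 and 2.5-3 points at 255-280 per arm, and truncation by eligibility makes the lower part plausible. Protection against chance imbalance, and a settled answer to which RR is primary, are at least as good reasons as the precision.

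This rests on the planned risks of 20% and 10%, a single normal covariate of assumed strength, and numeric IGRA readings being kept in the database. It does not change the stated sample size. Adjustment also does not cure the restriction in 6.6 of the intention-to-treat set to participants with at least six months of treatment, which is a different matter.

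**What to change.** Add a short paragraph to 6.6, fixed before the randomisation list is opened and preferably before the arm comparison at the interim analysis (6.7):

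- Primary estimate: a marginal RR, with ARR and NNT and their 95% CIs, standardised from one logistic model. The terms are arm; baseline interferon-gamma (the higher of TB1 and TB2, either untransformed or on the log scale with a stated floor for zero values); age; and one named incarceration variable from the criminal-history questionnaire.
- State one form for each covariate, with no alternatives left open, and one simple rule for missing covariate values that does not depend on arm.
- Keep the unadjusted RR as a sensitivity analysis.

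Standardisation leaves the target quantity a marginal RR. The cost is a few lines of text and slightly more analysis work, possibly a short script or bootstrap for the intervals. No new data collection is needed, provided the questionnaire holds a usable incarceration item, which should be confirmed first.

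### The analysis called intention-to-treat admits only participants who complete 6 months of treatment, and no relative-risk comparison of all randomised participants is specified

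*Combined protocol and SAP*

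**What the plan says.** Section 6.6 names two analyses, intention-to-treat and per protocol. The first is defined by "The intent-to-treat analysis will be performed for all subjects who complete at least 6 months of treatment". The second is defined by "Analysis by protocol will be performed only using the group of individuals who completed at least 80% of the predicted doses of the study". The same section says "The sample calculation for the primary outcomes is based on intention-to-treat analysis".

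Three other sentences bear on who is counted:

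- For partial withdrawal of consent, section 6.6 says "the participant will remain in the study according to the initial randomization".
- For incidence, it says "The incidence will be calculated on the basis of the new cases detected during the follow-up period, per 100 person-years", without naming a population.
- Section 6.5 adds that "the Notification of Injury Information System will be used to identify the occurrence of active TB cases in both groups".

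On follow-up, Figure 1 places randomisation at D0 and the first post-baseline IGRA at month 6 (± 15 days). IGRA and sputum at the early exclusion visit are optional. Section 6.4 describes staying in the study without DOT only for interruptions from month 6 onward.

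On events, a participant with a positive IGRA at a follow-up visit is handled so: "the participant will suspend the medication (in the case of the 6-month visit), will be excluded from the study and treatment for latent TB". Section 6.6 counts seroconversion on the "commercial test in the 12th or 24th month".

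**The concern.** An intention-to-treat set keeps everyone who was randomised in the arm assigned. Here membership is decided by something that happens over the six months after randomisation and that the assigned drug can influence. Section 6.4 lists exits that can fall before month 6: adverse events, interruptions totalling 90 days or more, non-compliance, transfer or release. At least the first can differ between isoniazid and placebo. If those who leave also differ in infection risk, the groups compared are no longer the randomised ones, and the RR, absolute risk reduction and NNT inherit the imbalance.

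The plan has no all-randomised analysis against which to check the restricted one. A result labelled intention-to-treat would be read as covering all 728, which it would not. The follow-up rules have the same gap: someone who leaves before month 6 may never have a post-baseline IGRA, and that cannot be recovered later.

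**Working it through.** **1. The sample-size figure.** Inputs from section 6.1.1 are 20% versus 10% at one year, 5% significance (taken as two-sided) and 90% power. The standard two-proportion formula gives a total of 532, or 572 with continuity correction. The plan states 560, within 3% of the latter. Power with 280 per arm is 91.4%, and 560 × 1.3 = 728, or 364 per arm. The sample size is not in dispute. It is said to rest on intention-to-treat, which the 6-month set is not.

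**2. Does any sentence restore an all-randomised comparison?**

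| Sentence | Effect on the 6-month limit |
|---|---|
| Partial consent withdrawal (6.6) | Keeps assigned arm; does not lift the limit |
| Person-years incidence (6.6) | States no limit, but names no population and does not define the RR |
| Notification search (6.5) | Active TB only; cannot supply the IGRA primary outcome |
| Per-protocol set (6.6) | Also selected on treatment received |

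None does.

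**3. Possible bias with an inert drug (all stopping inputs assumed).** Risk is 0.20 in each arm as randomised. A fraction f of the isoniazid arm only stops before month 6, and stoppers have k times the risk of stayers. Since 0.20 = (1 − f) × r + f × k × r, the stayers' risk is r = 0.20/(1 − f + fk), and the restricted RR is 1/(1 − f + fk). The last two columns give the chance of a significant result favouring isoniazid (two-sided 5% test, nominal 2.5% on that side, 364 controls against 364 × (1 − f), normal approximation).

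| f | RR, k = 2 | RR, k = 0.5 | False result, k = 2 | False result, k = 0.5 |
|---|---|---|---|---|
| 5% | 0.95 | 1.03 | 5.1% | 1.7% |
| 10% | 0.91 | 1.05 | 8.8% | 1.1% |
| 20% | 0.83 | 1.11 | 19% | 0.4% |

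Example: f = 0.10, k = 2 gives 1/(0.90 + 0.20) = 0.909. With stopping in both arms, 15% isoniazid and 5% placebo, the RR is 1.05/1.15 = 0.913 (k = 2) or 0.975/0.925 = 1.054 (k = 0.5). With 10% in each arm it is 1.00.

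**4. Possible bias when the true RR is 0.50.** The retained risk is (p − d × r)/(1 − d), where p is the arm's risk as randomised, d the share excluded and r their risk. Suppose 10% of controls (at 20% risk) and 15% of the isoniazid arm are excluded. If the excluded isoniazid participants have 15% risk, the retained risk is (0.10 − 0.15 × 0.15)/0.85 = 0.091 and the RR is 0.46. If they have 5% risk, it is (0.10 − 0.15 × 0.05)/0.85 = 0.109 and the RR is 0.54. Exclusion of 30% per arm unrelated to risk leaves 0.50.

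**5. Dilution is a separate matter.** If 15% of the isoniazid arm stop at month 3 and lose all protection, their risk is 0.10 × 3/12 + 0.20 × 9/12 = 0.175. The all-randomised risk is 0.85 × 0.10 + 0.15 × 0.175 = 0.111, so RR 0.56. If half the protection is kept, the stoppers' risk is 0.1375 and the RR is 0.53. This is a different estimand, not bias in the restricted set.

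**6. Month-6 conversions.** Section 6.7 assumes that risk accrues linearly. By month 6 about 364 × 0.10 = 36 control and 364 × 0.05 = 18 isoniazid conversions are expected, out of 73 and 36 by month 12. That is half. The plan removes these participants from the study and does not say that their conversions count. As the visit may fall up to 15 days early, a converter taken off medication then may also miss the 6-month threshold.

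**The case against.** The strongest objection concerns size. The trial is double-blind and placebo-controlled with observed dosing. Transfer and release should be largely independent of arm. Entry criteria screen out several liver risks. The documents' hepatotoxicity figures are low: 1% expected in section 6.9; 2.4% and 2.7% in two trials, an average of 6% in one review, and 0.52% against 0.12% in controls in another (section 2.5). In the step 3 formula with k = 2 and stopping in the isoniazid arm only, 1%, 2.7% and 6% give RRs of 0.99, 0.97 and 0.94 and false-positive chances of 2.9%, 3.7% and 5.7%. Nothing in the documents ties stopping to infection risk, so the factors 2 and 0.5 are assumptions.

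This stands as a caution on size: the bias may be small. But hepatotoxicity rates are not stopping rates, and the 30% allowance in section 6.1.1 covers losses of every kind, so the documents cannot show that it is small.

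Two further points stand in part. The month-6 converter problem is a conflict over outcome definition that would persist with a perfect all-randomised set; it needs fixing alongside, but does not measure the effect of the restriction. The month-6 wording in section 6.4 could be read in more than one way, and section 6.6 does not say how 6 months of treatment is measured, so the visit-window effect is possible rather than certain.

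None of this changes what section 6.6 says about the main set.

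**Conclusion.** The concern holds, and the definition must be corrected before analysis. The set called intention-to-treat is a modified set selected on treatment received after randomisation, and the plan specifies no RR on all randomised participants. This conclusion rests on the text alone and not on any forecast of bias.

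The size and direction of any bias cannot be known from the documents. Under the assumptions shown, an inert drug could give a restricted RR from 0.83 to 1.11 with 5% to 20% early stopping in the isoniazid arm only. If stopping is unrelated to arm or to risk, the main loss is of precision and generality.

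**What to change.** - **Primary set.** Define it as all randomised participants in their assigned arm, removing at most those whose pre-dose baseline culture proves positive.
- **Events.** Count an IGRA conversion observed at month 6 or at an exit visit as a primary-outcome event by month 12. Count active TB from any time after D0, including cases found through the notification system. Do not impute over observed events.
- **Follow-up.** Extend the existing option of attending visits without DOT to those who stop before month 6. Where consent allows, seek the scheduled IGRA and sputum, or an exit IGRA. Seek the exit IGRA from all leavers: if it is left to clinical judgement, ascertainment may be uneven.
- **Missing outcomes.** Handle only those truly missing, by a prespecified method such as multiple imputation by arm with a tipping-point sensitivity analysis. Report missingness by arm and reason.
- **Label.** Rename the 6-month set as modified and supportive.

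The cost is protocol and SAP wording, an event-counting rule, a missing-data paragraph and some extra follow-up at visits already scheduled. Results for early leavers will rely largely on imputation, because month 6 is the first scheduled post-baseline IGRA. The estimate may be less favourable. With 364 per arm, all outcomes observed and the planned 20% versus 10%, power is 96.7%. If 15% of the isoniazid arm stop early and carry the control risk (assumed), the isoniazid risk is 0.85 × 0.10 + 0.15 × 0.20 = 11.5% and power is 88.4%.
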